#### b) Visit OP2, the CMC visit, on the day of the "high" result or the next:

- Diary review, AEs, medications, and indications for a directed physical exam, wet mount, and other tests will be managed as described for Visit 2 (BP1).
- The participant will be asked whether she used condoms until Day 10 and then refrained from intercourse and the use of intravaginal products, and whether her male partner refrained from ejaculation since Day 10. If instructions were not followed, she will be reinstructed. If she used a spermicide or spermicidal lubricated condom since day 10, Visit OP2 will be rescheduled in the next cycle. Otherwise, the visit may continue at the investigator's discretion.
- The participant will undergo a pelvic exam:
  - o Signs of irritation of the external genitalia, cervix, and vagina, as observed with the naked eye, will be noted.

<sup>s "Other vaginal activity" includes insertion of vaginal medications/products other than the study product (prescription or over-the-counter), as well as insertion of sex toys, fingers, or anything else into the vagina. Tampons may be used during all days of menses in the Baseline PCT and Caya PCT cycles, but only during the first three days of menses in Ovaprene cycles.

Version: 06.00 (FINAL) Date: June 13, 2019

- o The position of the device relative to the cervix will be noted.
- o Cervical mucus will be examined for pH, ferrous gluconate, midcycle characteristics, and the presence of sperm (see **Appendix 2**).
- o Vaginal sample(s) will be collected for pH, ferrous gluconate, and the presence of sperm.
- o It is expected that the cervical mucus could be thick and should be without sperm at the CMC. If sperm are found in the vagina or cervical mucus, this cycle will be rescheduled and instructions on condom use and abstinence will be reviewed.
- o If no sperm are detected in the vagina or cervical mucus, the participant will be instructed to have intercourse without a condom but with the device in place, 2 to 3 hours prior to the next visit, which will be scheduled for the same or following day, within 27 hours of the mucus check visit.
- o The participant will be instructed to otherwise avoid any other vaginal activitiest until after Visit OP3.

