# c) Visit OP3, the PCT visit, 2-3 hours after intercourse and within 27 hours of the CMC:

The participant will return to the clinic 2-3 hours after coitus ends and within 27 hours of the mucus check visit.

- Diary review, AEs, medications, and indications for a directed physical exam, wet mount, and other tests will be managed as described for Visit 2 (BP1)
- An acceptability questionnaire will be administered.
- The participant will undergo a pelvic exam:
  - o Signs of irritation of the external genitalia, cervix, and vagina, as observed with the naked eye, will be noted.
  - o The position of the device relative to the cervix will be noted.
  - o Cervical mucus will be examined for pH, ferrous gluconate, midcycle characteristics, and the presence of sperm (see **Appendix 2**).
  - o Vaginal sample(s) will be collected for pH, ferrous gluconate, and the presence of sperm.
  - o At sites other than EVMS, vaginal samples will be collected for antibacterial activity and soluble markers.
  - Results of the test PCT will be interpreted as shown in Appendix 3. A successful test PCT will show mucus containing an average of <5 progressively motile sperm per HPF.
- At the EVMS site only:
  - o At 0.5, 1, 2, 4, and 6 hours after the PCT: u
    - Vaginal sample(s) will be collected for pH and ferrous gluconate.
  - o At 6 hours after the PCT, if possible:

<sup>t "Other vaginal activity" includes insertion of vaginal medications/products other than the study product (prescription or over-the-counter), as well as insertion of sex toys, fingers, or anything else into the vagina. Tampons may be used during all days of menses in the Baseline PCT and Caya PCT cycles, but only during the first three days of menses in Ovaprene cycles.

<sup>u Samples will be collected at as many of these timepoints as possible.

Version: 06.00 (FINAL) Date: June 13, 2019

- Vaginal sample(s) for antibacterial activity and soluble markers will be collected.
- The participant will be instructed to refrain from intercourse and other vaginal activity until after Visit OP4, 24 hours after Visit OP3.

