#### d) Visit OP4, 24 hours after the PCT:

- Diary review, AEs, medications, and indications for a directed physical exam, wet mount, and other tests will be managed as described for Visit 2 (BP1).
- The participant will undergo a pelvic exam:
  - o Signs of irritation of the external genitalia, cervix, and vagina, as observed with the naked eye, will be noted.
  - o The position of the device relative to the cervix will be noted.
  - o Vaginal sample(s) will be collected for ferrous gluconate and pH.
- Participants will be instructed as follows:
  - o Intercourse is permitted after this visit for the rest of this cycle with the following restrictions:
    - Condoms lubricated with something other than nonxynol-9 must be used (dispense as needed).
    - No sex or other vaginal activitym is permitted in the 72 hours prior to the final visit in the cycle.
  - O A tentative appointment will be made for the next visit, taking into account the participant's usual cycle length and the need to have that visit take place before the participant's next menses begins but as late as possible in the cycle. The participant will be instructed to contact the site immediately if it appears that her menses is starting before the tentatively scheduled appointment.

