<sup>9 Cervical Mucus Evaluation includes: midcycle characteristics and presence of sperm, see **Appendix 2.** 

<sup>10 EVMS only: Vaginal pH will also be tested at, 0.5, 1, 2, 4, and 6 hour time points, if possible.

<sup>11 Non-EVMS sites: Vaginal samples for antibacterial activity and soluble markers will be collected at the time of the PCT or OS1. At EVMS only, they will be collected only at 6 hrs, if possible.

<sup>12 EVMS only: Vaginal ferrous gluconate samples will also be collected at 0.5, 1, 2, 4 and 6 hours, if possible

<sup>13 The participant will insert Ovaprene™ using written instructions, with assistance if needed. The clinician will check the placement.

Version: 06.00 (FINAL) Date: June 13, 2019

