- c) Levels of ferrous gluconate in CVF before sex that are associated with fewer than 5 progressively motile sperm per HPF in the cervical mucus after sex (i.e. success), during ovulation. Summary statistics of sample size, mean, median, standard deviation, and IQR will be presented by visit.
- d) Levels of ferrous gluconate in CVF at multiple time points in the safety cycle in the absence of coitus. This will allow the estimation of how long after insertion it takes to reach the target concentration levels associated with success and whether target levels are still present up to 29 days after insertion. Summary statistics of sample size, mean, median, standard deviation, and IQR will be presented by visit and assessment timepoint.
- e) Levels of ferrous gluconate in CVF before and at multiple time points after sex at ovulation with the device in place. This will allow determination of whether they are different from before sex and, if so, how much time is needed to return to pre-sex levels at all visits in Ovaprene® PCT cycles in both vaginal and cervical fluid. Summary statistics of sample size, mean, median, standard deviation, and IQR will be presented by visit and assessment time-point.
- f) Vaginal pH (from Vaginal Sample CRF) and cervical pH (from Cervical Mucus CRF) before and after sex in the absence and presence of the device. Six-number summary for the observed values and difference between pre-sex and after sex will be presented by visit. For the study site (EVMS only) with multiple timepoints at a visit, the summary will be done at each timepoint. The average of pH values within each visit over the multiple timepoints will be calculated for each subject, and then be summarized. The goal of these assessments during the Ovaprene® safety cycle is to look at the effect of study device in the absence of sex.
- g) Residual amount of ferrous gluconate in Ovaprene® devices that have been worn over a cycle of use. Six-number summary statistics will be presented by visit and by duration of time the device was worn (1-7 days, 8-14 days, 15-21 days, 22-28 days and >28 days).
- h) Cervical mucus score. Summary statistics mean, median, standard deviation, and IQR will be presented by visit. The number and percent of subjects with cervical mucus score ≥ 10 in each Ovaprene cycle will also be presented. For the summary of cervical mucus score ≥ 10, cervical mucus data will only be used from the cycle that occurs after the highest OPK result for that cycle.

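### SAP 3.6 e) claims a time to return to pre-sex ferrous gluconate levels in cervical fluid that the sampling cannot give; for vaginal fluid the offset from sex is unstated and no within-woman change is planned.

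*SAP*

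**What the plan says.** SAP 3.6, secondary item e), covers FG before and after sex in the Ovaprene PCT cycles. It says the data will settle whether intercourse alters the levels. It adds that, where it does, they will show "how much time is needed to return to pre-sex levels at all visits in Ovaprene® PCT cycles in both vaginal and cervical fluid". The analysis it commits to is sample size, mean, median, SD and IQR by visit and time-point. Item f), on pH, goes further and summarises the difference between pre-sex and post-sex values.

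Protocol 9.5.1 sets the sampling:

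- **OP2 (before sex).** "Cervical mucus will be examined for pH, ferrous gluconate, midcycle characteristics, and the presence of sperm"; vaginal FG is taken as well.
- **OP3 (PCT visit).** Cervical and vaginal FG are each taken at the PCT. The timing is fixed by "The participant will return to the clinic 2-3 hours after coitus ends and within 27 hours of the mucus check visit". At EVMS only, further samples follow: "At 0.5, 1, 2, 4, and 6 hours after the PCT", and for these "Vaginal sample(s) will be collected for pH and ferrous gluconate".
- **OP4 (24 hours after the PCT).** "Vaginal sample(s) will be collected for ferrous gluconate and pH". No cervical sample is listed.
- **OP5 (about cycle day 28).** Cervical and vaginal FG are both taken again.

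Protocol Appendix 1 agrees. Its cervical FG row is blank at OP4, and footnote 12 reads "EVMS only: Vaginal ferrous gluconate samples will also be collected at 0.5, 1, 2, 4 and 6 hours, if possible". The serial cervical testing in footnote 8 is for pH, not FG. A footnote in Protocol 9.4.1 classes the cervical FG assay as exploratory throughout.

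**The concern.** Objective 2d (Protocol 5.2) and question 4 of the Introduction ask how long FG in cervicovaginal fluid takes to recover after sex. SAP item e) extends that question to cervical fluid, and three things stand in the way of an answer as written.

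1. The cervical samples are too far apart to locate a return.
2. The vaginal sampling clock starts at the PCT, while the question is about time since sex. The SAP lists an hour 0 among its EVMS time points (SAP 3.2) without saying how it relates to coitus.
3. Return to pre-sex level is a statement about each woman against her own OP2 value, but item e) plans only group summaries of levels. The EVMS serial samples are taken at as many times as possible, so different women may supply different times. A shift in the group median can then reflect who was sampled as well as recovery.

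At stake is whether the study report makes a recovery-time statement that its data can support.

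**Working it through.** No sample size, power or error rate is involved and the plan gives no figure to reproduce. The check compares the sampling schedule with the question and converts the clock.

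**Inputs**

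- Coitus to PCT: 2-3 h (Protocol 9.5.1 c).
- EVMS serial times: 0.5, 1, 2, 4 and 6 h after the PCT (Protocol 9.5.1 c).
- OP4: 24 h after the PCT (Protocol 9.5.1 d).
- OP3 on cycle day 15 and OP5 on cycle day 28 (Protocol Table 11, hypothetical 28-day cycle).

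**Step 1: cervical FG.** In a PCT cycle it is scheduled at OP1 (before insertion), OP2 (before sex), OP3 (once) and OP5.

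- Gap from OP3 to OP5: 28 - 15 = 13 days, and 13 x 24 = 312 h.
- OP5 in hours after sex: 312 + 2 = 314 to 312 + 3 = 315.

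If cervical FG at OP3 differs from OP2, its return can be placed only somewhere between 2-3 h and about 314-315 h after sex. OP5 is not a clean comparison either: the device has stayed in place for the 13 days between, and Protocol 9.5.1 d) permits further, condom-protected intercourse in that period. The OP3 minus OP2 change remains estimable, so the first half of the question (do levels differ after sex?) can be addressed.

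**Step 2: vaginal FG.** Hours after sex = hours after PCT + (2 to 3).

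| Hours after PCT | Hours after sex | Sites |
|---|---|---|
| 0 (OP3) | 2-3 | all |
| 0.5 | 2.5-3.5 | EVMS |
| 1 | 3-4 | EVMS |
| 2 | 4-5 | EVMS |
| 4 | 6-7 | EVMS |
| 6 | 8-9 | EVMS |
| 24 (OP4) | 26-27 | all |

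Nothing is observed in the first 2 h after sex, so a dip and recovery within that time would be missed. Each nominal time carries a 1 h spread. At EVMS the widest gap up to OP4 is 24 - 6 = 18 h. Elsewhere there are two values in the first 27 h or so, at 2-3 h and 26-27 h, and then OP5.

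**Step 3: the comparison planned.** Item e) names no change from OP2 and no criterion for having returned. SAP 3.1.3 defines change as the visit value minus Baseline, but nothing makes OP2 the baseline for FG. Item f) specifies the pre/post-sex difference for pH, so the method is already in the plan and is missing only for FG.

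**The case against.** The other side has a fair case, and parts of it stand.

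- **The cervical assay is exploratory, and the protocol never asked for a cervical return time.** Objective 2d, question 4 and endpoint 2c name cervicovaginal fluid, and the SAP tabulates FG in CVF (Tables 14.2.2.1) separately from FG in cervix (Tables 14.2.2.2). This stands. A reader might infer that a protocol objective is left unanswered. It is not: the over-reach is in the SAP's wording, and vaginal samples remain to address the objective.
- **Item e) computes no return time, so there is nothing to be biased.** This also stands. A reader might infer that every reported return time will be 2-3 h too short, by a factor of five to seven at the first serial time (2.5/0.5 = 5; 3.5/0.5 = 7). That holds only if a time after the PCT is taken for a time after sex. The protocol labels the clock as running from the PCT and gives the interval from coitus, and neither document says nominal time will be reported as time since sex. The ratio is large because the divisor is 0.5; the discrepancy is a bounded 2-3 h.
- **Pairing is partly protected.** Vaginal FG at OP2, OP3 and OP4 is required at all sites, EVMS and other sites are tabulated separately, sample sizes are shown, and by-subject listings are planned. This stands for the main visits. It does not cover the optional EVMS times, and a listing is not a planned summary of change. The separate table shells were not available and may already hold such columns.
- **Other sites are not limited to OP3 and OP4.** Vaginal FG is also taken at OP5 everywhere. That is correct, though OP5 is too late to time recovery.

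**Conclusion.** The concern holds in a limited form. The cervical return time claimed in SAP 3.6 e) cannot be estimated from the planned samples: after OP3 the next cervical value is about 13 days later. That figure rests on the Table 11 example and will vary with cycle length. For vaginal FG, return can be bracketed but not timed from sex without adding 2-3 h, and the SAP does not state the offset. The planned group summaries are weaker than the pre/post-sex difference the SAP already uses for pH.

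The documents do not show that the vaginal analysis is invalid or that recovery will be reported as faster than it was. They also do not show whether the clock time of intercourse is recorded, so exact hours since coitus cannot be promised.

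The weight is minor to moderate. The endpoint is descriptive and secondary, in a feasibility study aiming for about 25 completers, and the primary PCT result does not depend on it.

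**What to change.** Amend SAP 3.6 e) and Tables 14.2.2.1 and 14.2.2.2 (EVMS and non-EVMS versions):

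1. Limit the return-time question to vaginal fluid. For cervical FG, report only the paired OP3 minus OP2 change, marked exploratory.
2. For vaginal FG, add the within-woman change from, or ratio to, that cycle's OP2 value at OP3, at each EVMS time point and at OP4, with the number of women contributing to each. State what counts as being back at the OP2 level; the documents give no assay precision from which to suggest a tolerance here.
3. Label times as hours after the PCT and state the 2-3 h offset from coitus. Use actual hours since coitus if the clock time is recorded. Report a woman already at her OP2 level at OP3 as 'returned by 2-3 h after sex', not as returned at time 0.

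The cost is SAP wording and a few more table columns, with no new samples or visits. What is given up is the cervical return-time claim.

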The completed Ovaprene™ PCT study demonstrated proof of concept in terms of reducing the number of progressively motile sperm seen in cervical mucus with the device in place.¹ The new study of Ovaprene™

Version: 06.00 (FINAL) Date: June 13, 2019

described in this document has been designed to provide further evidence of changes in the PCT as a result of Ovaprene™ use. A Caya PCT cycle has been included to ensure that in this study population and at these sites, results that are expected to be observed in a PCT cycle with an approved vaginal barrier can be replicated.

In addition, the release of agents from Ovaprene™, safety, user acceptability, and fit will be assessed. All participants will undergo a baseline PCT cycle without the use of the device, one PCT cycle with Caya, and two modified PCT cycles with Ovaprene™. Additional data will be collected in an Ovaprene™ cycle without sex acts.

With regard to release, the study will address the following questions:

- 1) What are the levels of ferrous gluconate in cervicovaginal fluid (CVF) before sex that are associated with fewer than 5 progressively motile sperm per HPF in the cervical mucus after sex (i.e., success) during ovulation?
- 2) How long after insertion does it take to achieve these levels?
- 3) Are these levels still present after 24-35 days of use?
- 4) What is the level of ferrous gluconate in CVF after sex at ovulation with the device in place and, if different from before sex, how much time is needed to return to pre-sex levels?
- 5) Does the presence of the device affect vaginal pH compared with the absence of the device?
- 6) Is there residual ferrous gluconate in Ovaprene™ devices that have been worn over a cycle of use?

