#### 5.2 OBJECTIVES

- 1. Primary: Changes in PCT results due to device use
  - a) Demonstrate successful barrier performance, as defined in **Appendix 3** during Ovaprene™ use in women who were able to demonstrate good results in a baseline cycle. An average of fewer than 5 progressively motile sperm in the cervical mucus per high powered field (HPF) is considered indicative of acceptable barrier function.
- 2. Secondary: Release of active component from device
  - a) Determine the levels of ferrous gluconate in CVF before sex that are associated with fewer than 5 progressively motile sperm per high powered field (HPF) in the cervical mucus (i.e. success) after sex, during ovulation.
  - b) Determine how long after insertion it takes to reach these levels
  - c) Determine whether these levels are still present 27-29 days after device insertion
  - d) Determine the levels of ferrous gluconate in CVF after sex at ovulation with the device in place and if different from before sex, how much time is needed to return to pre-sex levels.
  - e) Demonstrate the device's effect on CVF pH.
  - f) Assess residual amount of ferrous gluconate in Ovaprene™ devices that have been worn over a cycle of use.
- 3. Secondary: Safety
  - a) Assess systemic and genital safety using traditional endpoints and Ovaprene-specific endpoints
- 4. Tertiary: Acceptability
  - a) Assess acceptability of Ovaprene™ when left in place as directed for 3 cycles.
- 5. Tertiary: Fit
  - a) Assess fit of Ovaprene™.
  - b) Assess ability of women to insert, position, and remove the device
  - c) Assess the position of Ovaprene™ before and after intercourse and the relationship of position to other endpoints

Version: 06.00 (FINAL) Date: June 13, 2019

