#### 14.2.3 Secondary Objective: Release of active component from device

The mean, median, SD, and IQR of ferrous gluconate values associated with fewer than 5 progressively motile sperm per HPF will be calculated across all women. The mean, median, SD, and IQR of ferrous gluconate values at each time point at which it is collected will also be calculated across all women. The mean, median, SD, and IQR of ferrous gluconate values in used devices will be calculated. The mean, median, SD, and IQR of cervical mucus and vaginal pH before and after sex in the absence of and the presence of the device will be calculated across all women.

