|                            | 
 
c) Levels of ferrous gluconate in CVF before and at multiple
time points after sex at ovulation with the device in place.
(Allows determination of whether they are different from
before sex and, if so, how much time is needed to return to
pre-sex levels.)
 
   | Ovaprene® PCT cycles  |
|                            | d) Cervicovaginal pH before and after sex in the absence and presence of the device   | Baseline PCT
cycle, Ovaprene®
PCT cycles                                |
|                            | e) Residual amount of ferrous gluconate in Ovaprene devices that have been worn over a cycle of use.  | Ovaprene® safety cycle and Ovaprene® PCT cycles                               |
| 3. Safety                  | a) Treatment-emergent AEs among female subjects during Ovaprene® use.   | Ovaprene® safety cycle & Ovaprene® PCT cycles                                 |
|                            | b) Urogenital, product-related, and/or serious AEs among female and male subjects during Ovaprene® use.   | Ovaprene® safety cycle & Ovaprene® PCT cycles                                 |
|                            | c) Changes from baseline in complete blood count, serum chemistries, and serum ferritin   | Ovaprene® safety cycle  |
|                            | d) Changes from baseline in findings on pelvic exam, including colposcopy.  | Ovaprene® safety cycle & Ovaprene® PCT cycles                                 |
|                            | 
 
e) Changes from baseline in:
 
Nugent score and microflora
 
Antibacterial (anti-E. coli) activity in CVF
 
Soluble markers of inflammation in CVF
 
   | Ovaprene® safety cycle & Ovaprene® PCT cycles                                 |
|                            | f) Presence of Staphylococcus aureus or group A Streptococcus on Ovaprene® devices that have been worn over a cycle of use  | Ovaprene® safety cycle & Ovaprene® PCT cycles                                 |

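### SAP 3.6 f) names no within-woman pH change between device and no device, so the pH objective rests on by-visit levels set side by side

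*SAP*

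**What the plan says.** - **Objective.** Protocol 5.2, objective 2 e): "Demonstrate the device's effect on CVF pH". Release question 5 in Protocol section 4 puts it as a contrast: "Does the presence of the device affect vaginal pH compared with the absence of the device".
- **Endpoint.** Protocol section 6 and SAP 2.4, release endpoint d): "Cervicovaginal pH before and after sex in the absence and presence of the device".
- **Protocol analysis.** Section 14.2.3 plans four descriptive statistics (mean, median, SD, IQR) for "cervical mucus and vaginal pH before and after sex in the absence of and the presence of the device". These are levels. Table 14, which pairs baseline with comparison visits for other measures, does not list pH.
- **SAP analysis.** Section 3.6, secondary f): "Six-number summary for the observed values and difference between pre-sex and after sex will be presented by visit". At EVMS, where some visits have repeated samples, each time point is summarised, and in addition: "The average of pH values within each visit over the multiple timepoints will be calculated for each subject, and then be summarized". The item closes: "The goal of these assessments during the Ovaprene® safety cycle is to look at the effect of study device in the absence of sex".
- **Displays.** Tables 14.2.2.3 (cervical) and 14.2.2.4 (vaginal) are titled as pH values. The one planned graph plots vaginal pH over collection time at EVMS.
- **Other measures.** SAP 3.6 e) specifies the within-woman sperm change from BP2 to OP3A and to OP3B. SAP 3.7.6 specifies BP1 to OS1, BP2 to OP3 and OP1 to OP3 for antibacterial activity and soluble markers.

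**The concern.** The question is device versus no device. The difference named in f) is after sex versus before sex within a cycle, which answers a different question. Nothing in the pH text links a no-device visit to a device visit in the same woman, although the SAP does exactly that for sperm count and for soluble markers.

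At stake is how well the pH objective is answered. Acid release is part of the device description in Protocol section 4, and that section gives possible acid thickening of the mucus as the reason for reading Ovaprene PCTs differently. A clear estimate of the pH change, with its spread across women, would be useful background to that choice.

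**Working it through.** The plan states no pH figure and no power calculation, so there is nothing to reproduce. The check sets the texts side by side and then shows what the planned summaries leave out.

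**1. Which pH differences are named?** Protocol 14.2.3: none. Protocol Table 14: none. SAP 3.6 f): one, pre-sex versus after sex. SAP 3.1.3 has a general change-from-baseline formula, but no pH baseline visit is named and f) does not invoke it. No device versus no-device pH change is specified.

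**2. Which matched samples exist?** From Protocol section 9 and Appendix 1:

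| Situation | No device | Device | pH at both |
|---|---|---|---|
| At high OPK result, before sex | BP1 | OP2A, OP2B | vaginal and cervical |
| 2-3 hours after sex | BP2 | OP3A, OP3B | vaginal and cervical |
| Safety cycle, no sex | OS1 before insertion | OS2 to OS5 | vaginal at all four; cervical at OS3 and OS5 only |

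**3. Can the by-visit summaries stand in for the change?** For the mean, yes, if the same women are at both visits. For the spread, no. Take five women with pH 4.0, 4.5, 5.0, 5.5, 6.0 without the device (mean 5.0) and the values 3.5, 4.0, 4.5, 5.0, 5.5 with it (mean 4.5); the SD is 0.79 at each visit.
- Matched in that order, every change is -0.5: mean -0.5, SD 0.00.
- Matched in reverse order, the changes are 1.5, 0.5, -0.5, -1.5, -2.5: mean -0.5, SD = sqrt((4+1+0+1+4)/4) = 1.58.

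The by-visit tables are identical in the two cases. In the first every woman falls by the same amount; in the second two of five rise.

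**4. What does pairing do to precision?** Illustration only: the documents give neither an SD nor a correlation for pH. Assume n = 25 (the planned completers), SD 0.6 and within-woman correlation rho.
- Visits treated as two separate groups, which is all the by-visit n, mean and SD allow: t(48) × 0.6 × sqrt(2/25) = 2.011 × 0.170 = 0.34.
- Paired: t(24) × 0.6 × sqrt(2(1 - rho)/25), with t(24) = 2.064. rho 0.3: 2.064 × 0.142 = 0.29. rho 0.5: 2.064 × 0.120 = 0.25. rho 0.7: 2.064 × 0.093 = 0.19.

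The plan calls for neither interval.

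**5. Are the EVMS within-visit averages comparable?** Not for this purpose. At BP2, cervical pH is repeated from 0.5 to 6 hours after the PCT. At OP3, only vaginal pH is repeated. A cervical average would therefore cover several hours at one visit and a single sample at the other. At OS1, pH is taken before insertion and again 0.5 to 6 hours after it; if hour 0 enters the average, it mixes no-device and device values.

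**The case against.** The SAP follows the protocol's own analysis text. The endpoint and Protocol 14.2.3 ask for descriptive levels, the study was not sized on statistical grounds, and even the primary change from baseline is assessed qualitatively. Item f) also says that the safety-cycle pH is meant to show the device effect without sex, and it reports levels before and after insertion. All of that stands, and it keeps the point small.

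A reader might infer four stronger things that the documents do not support:

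- *That the plan yields no estimate of the device's pH effect.* The by-visit means give a crude one, and the by-subject listings keep the pairing available.
- *That dropout makes the compared means rest on different women throughout.* SAP 3.6 restricts these analyses to women with at least one completed Ovaprene PCT cycle, and enrolment requires a successful baseline cycle. For the first PCT cycle the women are nearly the same. The mismatch is confined to the second cycle, missed samples and cycles excluded as invalid.
- *That OS3 against BP1 is a clean midcycle pair.* OS3 is tied to a high OPK result only where possible; otherwise it falls 7-9 days after insertion. Pre-insertion OS1 is the better reference for that cycle.
- *That PCT classification depends on this contrast.* The reading rule in Protocol Appendix 2 does not use pH.

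The table shells are a separate document and might contain a change column, but the SAP names no pH contrast for them to implement.

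**Conclusion.** The gap is real and minor. The stated objective is the device's effect on pH. The only pH difference specified is for intercourse, so the device effect is available only as a crude comparison of levels, without a within-woman change, its spread or its uncertainty. For the second PCT cycle, or with missing samples, even that comparison may involve different women.

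The textual finding needs no assumption. The precision figures rest on an assumed SD of 0.6 and correlations of 0.3 to 0.7; they show the direction and rough size of what pairing gains, not a defect in a planned interval. The change is worth making because it costs almost nothing and brings pH into line with how the SAP treats sperm count and soluble markers.

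**What to change.** Add to SAP 3.6 f), and as rows in Tables 14.2.2.3 and 14.2.2.4, these within-woman changes:

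- OP2A minus BP1 and OP2B minus BP1, vaginal and cervical pH.
- OP3A minus BP2 and OP3B minus BP2, vaginal and cervical pH, using the first (PCT-time) sample at each visit.
- OS2, OS3, OS4 and OS5 each minus pre-insertion OS1 for vaginal pH; OS3 and OS5 only for cervical pH.

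Report n, mean, median, SD, IQR and a 95% confidence interval labelled as descriptive. State that the EVMS within-visit averages are not used for these contrasts. Keep the before/after-sex difference as a separate question.

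The cost is a few lines of SAP text and some table rows. No sample, visit or procedure changes.
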